10.3.2 Secondary endpoints

Confirmatory secondary endpoints

NA

Supportive secondary endpoints

Main period:

Effect

Endpoint title	Time frame	Unit
Change in height SDS	From baseline (week 0) to visit 6 (week 26)	-10 to +10
Change in HV SDS	From baseline (week 0) to visit 6 (week 26)	-10 to +10

Pharmacodynamics

Endpoint title	Time frame	Unit
Change in IGF-I SDS	From baseline (week 0) to visit 6 (week 26)	-10 to +10
Change in IGFBP-3 SDS	From baseline (week 0) to visit 6 (week 26)	-10 to +10

Protocol
Trial ID: NN8640-4245
UTN: U1111-1207-9741
EudraCT Number: 2018-000232-10~~CONFIDENTIAL~~Date:
Version:
Status:
Page:12 June 2020
7.0
Final
52 of 102**Novo Nordisk**

The analysis of change in HV SDS, change in height SDS and change in bone age is based on FAS and the ‘in-trial’ observation period. The analysis of change in IGF-I SDS and change in IGFBP-3 SDS is based on FAS and the ‘on-treatment’ observation period.

Height SDS will be derived using Centres for Disease Control and Prevention (CDC) standards²⁴ and HV SDS will be derived using Prader standards²⁵ as reference data.

The secondary endpoints: change in height SDS, HV SDS, IGF-I SDS and IGFBP-3 SDS from baseline will be analysed using MMRM on available assessments from planned visits with baseline assessment as covariate and treatment, age group, sex, region and sex by age group interaction term as factors, all nested within week as a factor. An unstructured covariance matrix will be used to describe the variability for the repeated measurements for a subject.

Extension I period:

Endpoint title	Time frame	Unit
Change in bone age	From baseline (week 0) to visit 8 (week 52)	Years

Bone age will be analysed using an ANCOVA model on change from baseline in bone age/chronological age assessed at week 52 and the model will include treatment, age group, sex, region and sex by age group interaction term as factors and baseline bone age/chronological age as a covariate. The treatment difference estimate will be reported with corresponding 95% CI and p-value. Subjects without post-randomisation data for the analysed endpoint will not be included in the analysis.

Supportive secondary safety endpoints

Endpoint title	Time frame	Unit
Change in fasting plasma glucose	From screening (visit 1) to visit 6 (week 26)	mmol/l
Change in HOMA	From screening (visit 1) to visit 6 (week 26)	%
Change in HbA1c	From screening (visit 1) to visit 6 (week 26)	% point

The safety endpoints will be analysed using descriptive statistics based on the corresponding ‘on-treatment’ observation period.

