Attachment I Global list of key staff and relevant departments and suppliers

Attachment II Country list of key staff and relevant departments, if applicable for the individual country

Protocol
Trial ID: NN8640-4245
UTN: U1111-1207-9741
Eudract Number: 2018-000232-10~~CONFIDENTIAL~~Date:
Version:
Status:
Page:12 June 2020
7.0
Final
6 of 102**Novo Nordisk**

1 Synopsis

Rationale

The purpose of this phase 2 dose-finding trial is to evaluate effect, safety and tolerability of once-weekly subcutaneous treatment of somapacitan compared to daily subcutaneous growth hormone (Norditropin®) treatment in children with short stature born small for gestational age with no catch-up growth by 2 years of age or older. **CCI**

The trial is a dose-finding, randomised, multinational, multi-centre, open-labelled active-controlled, parallel group design with a once weekly somapacitan dose regimen. Dosing somapacitan once weekly can potentially provide greater convenience, and thus potentially better adherence, compared to standard growth hormone treatment which must be administered daily. Treatment with growth hormone of children with short stature born small for gestational age with no catch-up growth by 2 years of age or older aims to induce growth, increase height velocity and improve final height.

Objectives and endpoints

Primary objective

To evaluate the effect of somapacitan versus Norditropin® on longitudinal growth in children with short stature born small for gestational age with no catch-up growth by 2 years of age or older.

Primary endpoint

Endpoint title	Time frame	Unit
Height velocity	From baseline (week 0) to visit 6 (week 26)	cm/year

Secondary objective

To evaluate the effect and safety of somapacitan versus Norditropin® in children born small for gestational age with no catch-up growth by 2 years or older.

Key secondary endpoints

Effect

Endpoint title	Time frame	Unit
Change in bone age	From baseline (week 0) to visit 8 (week 52)	Years
Change in height Standard Deviation Score	From baseline (week 0) to visit 6 (week 26)	-10 to +10
Change in Height velocity Standard Deviation Score	From baseline (week 0) to visit 6 (week 26)	-10 to +10

Protocol
Trial ID: NN8640-4245
UTN: U1111-1207-9741
Eudract Number: 2018-000232-10~~CONFIDENTIAL~~Date:
Version:
Status:
Page:12 June 2020
7.0
Final
7 of 102**Novo Nordisk****Safety**

Endpoint title	Time frame	Unit
Change in fasting plasma glucose	From screening (visit 1) to visit 6 (week 26)	mmol/l

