The randomisation will be stratified by region (Japan versus rest-of-the-world). The randomisation will additionally be stratified by age (< 6 versus \geq 6 years) and by gender (boys versus girls) within the rest of the world to ensure equal distribution of these factor levels across treatments.

Key Inclusion criteria

- Pre-pubertal children:
 - a) Boys:
 - Age \geq 2 years and 26 weeks and < 11.0 years at screening.
 - Testes volume < 4 ml.
 -
 - b) Girls:
 - Age \geq 2 years and 26 weeks and < 10.0 years at screening.
 - Tanner stage 1 for breast development (no palpable glandular breast tissue).
- Born small for gestational age (birth length and/or weight < -2 standard deviation scores) (according to national standards).
- Impaired height defined as at least 2.5 standard deviations below the mean height for chronological age and gender at screening according to the standards of Centers for Disease Control and Prevention at screening.
- Impaired height velocity defined as annualised height velocity below the 50th percentile for chronological age and gender according to the standards of Prader calculated over a time span of minimum 6 months and maximum 18 months prior to screening.
- No prior exposure to growth hormone therapy or Insulin-like Growth Factor-I (IGF-I) treatment.

Key exclusion criteria

- Any known or suspected clinically significant abnormality likely to affect growth or the ability to evaluate growth with standing height measurements.
- Children with hormonal deficiencies including suspected or confirmed growth hormone deficiency according to local practise.
- Current inflammatory diseases requiring systemic corticosteroid treatment for longer than 2 consecutive weeks within the last 3 months prior to screening.
- Children requiring inhaled glucocorticoid therapy at a dose of greater than 400 μ g/day of inhaled budesonide or equivalents for longer than 4 consecutive weeks within the last 12 months prior to screening.
- Concomitant administration of other treatments that may have an effect on growth, e.g but not limited to methylphenidate for treatment of attention deficit hyperactivity disorder.
- Diagnosis of attention deficit hyperactivity disorder.
- Prior history or presence of malignancy including intracranial tumours.

Protocol
Trial ID: NN8640-4245
UTN: U1111-1207-9741
Eudract Number: 2018-000232-10

~~CONFIDENTIAL~~

Date:
Version:
Status:
Page:

12 June 2020
7.0
Final
9 of 102

Novo Nordisk

Number of subjects:

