5.5 Justification for dose

CCI

Protocol
Trial ID: NN8640-4245
UTN: U1111-1207-9741
Eudract Number: 2018-000232-10

CONFIDENTIAL

Date: 12 June 2020 | ***Novo Nordisk***
Version: 7.0
Status: Final
Page: 25 of 102

Both treatments will be administered s.c. as this is the approved administration route for Norditropin® and is the intended route of administration for somapacitan.

The dose in the extension II period will be based on totality of evidence from the main period.

For UK: see [Appendix 9](#)

Protocol
Trial ID: NN8640-4245
UTN: U1111-1207-9741
EudraCT Number: 2018-000232-10

~~CONFIDENTIAL~~

Date:
Version:
Status:
Page:

12 June 2020
7.0
Final
26 of 102

Novo Nordisk

6 Trial population

Prospective approval of protocol deviations to recruitment and enrolment criteria, also known as protocol waivers or exemptions, is not permitted.

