10.3.5 Other analyses

Annualized HV at 13 weeks, 26 weeks, 39 weeks and 52 weeks will be analysed using a MMRM with treatment, age group, sex, region and sex by age group interaction term as factors and height at baseline as a covariate, all nested within week as a factor. An unstructured covariance matrix will be used to describe the variability for the repeated measurements for a subject. From the MMRM the treatment differences at week 52 weeks will be estimated for the same treatment contrasts as for the primary analysis of the primary endpoint.

Height profiles will be presented by subject with time point for treatment switch in the extension II period (if applicable) and start of puberty (if applicable) indicated in the graphs. Annualised HV for the second year in trial will be derived as: (height at 104 weeks visit – height at 52 weeks visit) / (time from 52 weeks visit to 104 weeks visit in years). Annualised HV for the second year in trial will be analysed using descriptive statistics by treatment arm (treatment arm from main trial period), as well as by extension II period treatment arm. Annualised HV for third, fourth and fifth year in trial will be derived analogously and analysed using descriptive statistics.

Change in height SDS, HV SDS, IGF-I SDS and IGFBP-3 SDS from baseline to week 52 will be analysed using an MMRM on available assessments from planned visits similar to the MMRM used for the analysis of week 26 data, with baseline assessment as covariate and treatment, age group, sex, region and sex by age group interaction term as factors, all nested within week as a factor.

IGF-I SDS and IGFBP-3 SDS data from extension II will be analysed using descriptive statistics.

Protocol
Trial ID: NN8640-4245
UTN: U1111-1207-9741
EudraCT Number: 2018-000232-10~~CONFIDENTIAL~~Date:
Version:
Status:
Page:12 June 2020
7.0
Final
54 of 102**Novo Nordisk**

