Adverse events will be analysed using descriptive statistics based on the ‘on –treatment’ observation period within the main trial period (26 weeks of treatment). The adverse events will be summarised by treatment, MedDRA (Medical Dictionary for Regulatory Activities) system organ class and MedDRA preferred term. The descriptive statistics will include the number and percentage of subjects who experienced adverse events, the number of events and rate. AEs will be listed by treatment and subject with information on severity, relationship to trial product and demographics based on the ‘on –treatment’ observation period. Adverse events with onset 14 days or more after last trial drug administration will be reported in a separate listing. AEs with onset before first dosing will be reported in a separate listing.

Similar tables will be made for AEs in the extension trial periods (I and II).

Muscle, fat and bone parameters measured using bioelectrical impedance analysis will be analysed using descriptive statistics based on the ‘on –treatment’ observation period within the main trial period.

Analogous analysis will be made for the muscle, fat and bone parameters assessed in the extension trial periods (I and II).

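### Week-52 bone age is declared in years, but the only planned model analyses bone age/chronological age, so under the natural ratio reading no treatment difference in years is reported

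*Combined protocol and SAP*

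**What the plan says.** The Synopsis, section 4.3.2.3 and the Extension I table in section 10.3.2 all list change in bone age, week 0 to visit 8 (week 52), with the unit years. Section 10.3.2 uses the same name when it assigns the analysis set: "The analysis of change in HV SDS, change in height SDS and change in bone age is based on FAS".

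The model follows directly below the Extension I table: "Bone age will be analysed using an ANCOVA model on change from baseline in bone age/chronological age assessed at week 52". Its factors are treatment, age group, sex, region and sex by age group, and its covariate is baseline bone age/chronological age. On output the section says: "The treatment difference estimate will be reported with corresponding 95% CI and p-value". The document does not define bone age/chronological age.

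Section 9.1.3 allows an X-ray taken up to 13 weeks before screening to serve as the baseline image.

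**The concern.** The declared quantity and the modelled quantity differ. If the slash means a ratio, the estimate, interval and p-value have no unit, yet they would be reported under an endpoint titled in years. A reader looking for how many years of bone age separate two arms would not find it.

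This is the only listed endpoint that measures skeletal maturation, and the Synopsis lists it among the key secondary endpoints. The X-rays would allow an analysis in years later. Its covariates and its handling of X-ray timing would then be chosen without pre-specification, possibly after the sponsor has been unblinded at the main-period database lock (section 10.3.4).

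**Working it through.** The plan gives no SD, expected difference or power for bone age, so there is no planned figure to reproduce. The sample size calculation in section 10.1 concerns height velocity only.

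**1. Is a difference in years planned elsewhere?** Section 10.3.5 adds week-52 models for annualised height velocity and for four scores: "Change in height SDS, HV SDS, IGF-I SDS and IGFBP-3 SDS from baseline to week 52 will be analysed using an MMRM". Bone age is not among them. The section also mentions bone parameters, but these are not X-ray bone age: "Muscle, fat and bone parameters measured using bioelectrical impedance analysis will be analysed using descriptive statistics". No model or descriptive summary in years was found.

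**2. What each reading of the slash gives.** Let BA be bone age and CA chronological age, with 0 for baseline and 52 for week 52.
- Ratio: R = BA52/CA52 − BA0/CA0. The treatment difference in R is unitless.
- Difference: (BA52 − CA52) − (BA0 − CA0) = change in BA − change in CA. The treatment difference is in years, because elapsed time averages out between randomised arms.

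The ratio is the natural reading of the notation, but only a definition would settle it.

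**3. Per-child sensitivity of the ratio.** With baseline values held fixed, d extra years of bone age at week 52 change R by d/CA52, where CA52 = CA + 1 and CA is age at week 0. The ages come from inclusion criterion 2; for boys it reads "2 years and 26 weeks and < 11.0 years at screening", and the girls' upper limit is 10.0. Screening age is taken as baseline age.

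| Baseline age | Ratio change per year, 1/(CA+1) | Years per 0.01 of ratio, 0.01 × (CA+1) |
|---|---|---|
| 2.5 | 1/3.5 = 0.286 | 0.035 |
| 6 | 1/7 = 0.143 | 0.07 |
| just under 10 | 1/11 = 0.091 | 0.11 |
| just under 11 | 1/12 = 0.083 | 0.12 |

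The factor varies 0.286/0.083 = 3.4-fold across eligible ages.

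**4. What this means for the arm-level estimate.** The model reports a mean difference between arms. If the effect is d years at every age, the expected ratio difference is d × mean(1/CA52), which is a single factor.
- Large-sample check, assuming ages uniform from 2.5 to 11, mean BA/CA of 0.85 and d = 0.3 year: the ratio ANCOVA gave 0.0434. Mean(1/CA52) = ln(12/3.5)/8.5 = 0.145, and 0.0434/0.145 = 0.30 year.
- At trial size, assuming ages uniform from 2.5 to 11 (boys) or 10 (girls), BA = 0.85 × CA plus noise with SD 1.0, follow-up noise with SD 0.5 and d = 0.5 year: the converted estimate averaged 0.490, 0.497 and 0.496 year with 8, 11 and 12 children per arm.

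So conversion works if the effect in years is constant across ages and the trial's age distribution is available. If the effect varies with age, the ratio gives younger children more weight and no single factor recovers the mean effect in years.

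**5. X-ray interval.** An image taken 13 weeks before screening makes the interval to week 52 at least 52 + 13 = 65 weeks, plus the time from screening to week 0. A raw change in years then includes at least 13/52 = 0.25 year more elapsed time than a baseline image taken at week 0.

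**The case against.** The ratio of bone age to chronological age is a legitimate scale, its comparison between randomised arms is valid, and using age at each X-ray would partly allow for an early baseline image. All of that stands.

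The slash might also mean a difference, in which case the estimate would already be in years. That is possible, and it is why the definition comes first in the fix. The text would still need to say so.

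Two stronger readings are tempting, and the documents support neither. A reader might infer from the 3.4-fold spread that the ratio result can never be turned into years. The spread is a per-child sensitivity, and step 4 shows that approximate conversion is possible under a constant effect. A reader might also infer that the ratio model is biased or could give the opposite sign. The two scales can disagree in sign if the effect itself changes sign with age, but nothing in the documents suggests such an effect.

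Finally, the endpoint is supportive, in an exploratory phase 2 trial without multiplicity adjustment (section 10.3). That limits the weight of the point but does not remove the mismatch.

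**Conclusion.** The point holds as a mismatch between endpoint and analysis, conditional on reading the expression as a ratio. Under that reading the plan leaves its endpoint in years without a treatment difference in years. The reported ratio result could be converted only approximately, under the two conditions in step 4; the documents neither state nor exclude a constant effect.

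The consequence is modest. The primary conclusion concerns height velocity at week 26. The extension II dose does not draw on week-52 bone age: "The dose in the extension II period will be based on totality of evidence from the main period". The mismatch should still be corrected, because it is plain from the text and cheap to repair.

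**What to change.** In section 10.3.2:
1. Define bone age/chronological age as a ratio or a difference, with chronological age taken at the date of each X-ray.
2. Add an ANCOVA on change in bone age in years at week 52, with the existing factors and baseline bone age as covariate. Report the treatment difference in years with its 95% CI.
3. State how the varying X-ray interval is handled, for example by including the time between X-rays as a covariate.
4. Keep the ratio model as an additional analysis.

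If the ratio is the intended endpoint, change the title and unit instead in the Synopsis, section 4.3.2.3 and section 10.3.2.

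The cost is one more model on X-rays already scheduled, or a wording change. Baseline chronological age may be added as a second covariate but is not needed to match the endpoint. If it is added, its own coefficient will be unstable (median variance inflation factor about 7 to 15), but the standard error of a treatment difference widens by only 1.0% to 1.7% on average, before any gain in precision. Those figures come from simulation and assume 8 to 12 children per arm, ages uniform over the eligible range, a correlation of 0.82 to 0.94 between bone age and chronological age, and 20% of children from Japan. Where only year of birth is recorded (Spain and Switzerland, Appendix 9), chronological age is approximate; the planned ratio has the same limitation.

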4.1.2 Secondary objective

To evaluate the effect and safety of somapacitan versus Norditropin® in children with short stature born SGA with no catch-up growth by 2 years of age or older.

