4.3.2.4 Safety

Endpoint title	Time frame	Unit
Change in fasting plasma glucose	From screening (visit 1) to visit 6 (week 26)	mmol/l
Change in homeostatic model assessment (HOMA)	From screening (visit 1) to visit 6 (week 26)	%
Change in Glycated haemoglobin (HbA1c)	From screening (visit 1) to visit 6 (week 26)	% point

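### The safety objective is comparative, but fasting glucose, HOMA and HbA1c are only summarised by arm: no between-treatment difference, confidence interval or adjustment for the screening value is planned

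*Combined protocol and SAP*

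**What the plan says.** Section 4.1.2 gives the secondary objective as "To evaluate the effect and safety of somapacitan versus Norditropin® in children with short stature born SGA" without catch-up growth. Section 4.3.2.4 lists three safety endpoints, each a change from screening (visit 1) to visit 6 (week 26): fasting plasma glucose, HOMA and HbA1c. The synopsis puts them under its key secondary endpoints.

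Their analysis is one sentence in 10.3.2: "The safety endpoints will be analysed using descriptive statistics based on the corresponding" on-treatment observation period. Section 10.2 assigns safety endpoints to the SAS. Section 10.3.5 handles adverse events in the same way: "Adverse events will be analysed using descriptive statistics based on the" on-treatment period, by treatment.

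The other supportive secondary endpoints are modelled. Section 10.3.2 states: "The secondary endpoints: change in height SDS, HV SDS, IGF-I SDS and IGFBP-3 SDS from baseline will be analysed using MMRM", with the baseline value as covariate and treatment, age group, sex, region and sex by age group as factors. Bone age gets an ANCOVA with the same factors and its own baseline covariate, and the treatment difference is to be reported with a 95% CI and p-value. For the primary endpoint, 10.3.1 names four somapacitan-Norditropin® contrasts and says that conclusions rest on confidence intervals, not tests.

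**The concern.** The objective asks for a comparison, and for these endpoints the analysis stops one step short of it. A reader who wants the comparison has to subtract arm means based on about 11 or 12 children, with no measure of how uncertain the result is. Two arms with similar mean changes could then be taken as evidence of similar glucose metabolism when the data are too few to show it.

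This has some practical weight because sections 5.1 and 5.5 base the extension II dose on the main-period evidence as a whole. As planned, that evidence has interval estimates for growth differences between products but none for glucose differences.

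**Working it through.** **1. Is there a structural reason for the different treatment?**
- Analysis sets: FAS and SAS have the same definition in 10.2 (randomised and exposed, analysed as treated).
- Observation period: IGF-I SDS and IGFBP-3 SDS also use the on-treatment period, yet get a baseline-adjusted MMRM.
- Status: bone age is also a supportive secondary endpoint, yet gets an ANCOVA with a CI.
- Data: screening and week-26 values of the three safety endpoints are already collected.

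Nothing in the plan explains the difference.

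**2. The plan's own figure.** The only sample-size figures concern height velocity. With 11 per arm, SD 2.6 and a difference of 3.25 cm/year, the noncentrality is 3.25 / (2.6 × √(2/11)) = 2.93. A two-sided 5% t-test with 20 df then has 79.6% power, against 80% stated. This confirms 11 per arm as the planning number. The documents give no SD or correlation for glucose, HOMA or HbA1c, so what follows is in SD units, with the screening to week-26 correlation r **assumed** to be 0.3 to 0.7 and variances equal at the two times.

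**3. What the change score leaves uncorrected.** If two arms differ by d at screening, the expected difference in mean change shifts by −(1−r)d. A one-standard-error imbalance with 12 per arm is d = √(2/12) = 0.41 SD. The shift is then 0.7 × 0.41 = 0.29 SD at r = 0.3 and 0.3 × 0.41 = 0.12 SD at r = 0.7. Using the screening value as covariate removes this.

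**4. Gain in variance.** In large samples the ratio of adjusted to unadjusted variance is (1−r²) / (2(1−r)) = (1+r)/2, that is 0.65, 0.75 and 0.85 for r = 0.3, 0.5 and 0.7. Small samples give some of this back. The model estimates five covariate terms (screening value, age group, sex, region, sex by age group) beside five arm means. With 55 children the approximate inflation is 1 + 5/(55−5−5−1) = 1.114:

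| r | (1+r)/2 | × 1.114 |
|---|---|---|
| 0.3 | 0.65 | 0.72 |
| 0.5 | 0.75 | 0.84 |
| 0.7 | 0.85 | 0.95 |

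A simulation of the full ANCOVA (11 or 12 per arm, non-prognostic factors, an assumed 15% of children in Japan) gives ratios from 0.72 to 0.94, a saving of about 28% down to 6%. It did not stratify the factors; the trial's stratification would make the loss somewhat smaller, and prognostic factors would add to the gain.

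**5. Precision of the added contrast.** The ANCOVA has 10 parameters, so 55 − 10 = 45 residual df. The pairwise 95% half-width is t(0.975, 45) × √(2/11) = 2.014 × 0.426 = 0.86 residual SDs. In units of the week-26 SD, multiply by √(1−r²): 0.82, 0.74 and 0.61 for r = 0.3, 0.5 and 0.7. The range is about 0.6 to 0.9 SD, before the small loss from covariate imbalance in step 4.

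**The case against.** The strongest reply is that this is ordinary phase 2 safety reporting. Section 10.3 calls the trial exploratory and makes no multiplicity adjustment. Section 4.3.2.1 names no confirmatory secondary endpoints, the sample size was set for height velocity alone, and an objective to evaluate safety does not promise a modelled difference. Intervals with half-widths of 0.6 to 0.9 SD may change no decision, and the gain from adjustment is close to nil at the upper end of the assumed correlations. All of this stands, and it is why the point is minor. It does not explain why equally small arms are modelled for the other supportive secondary endpoints, and imprecision is a reason to show an interval.

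Three stronger readings are tempting, and the documents do not support them:
- **That a screening imbalance goes uncorrected.** The endpoints are changes from screening, so the screening value is subtracted within each child. Only regression to the mean remains.
- **That safety gets no estimate.** By-arm mean changes, and adverse-event counts, percentages and rates, are estimates from concurrent randomised arms. What is not planned is a contrast with an interval.
- **That the safety objective fails or the trial is invalid.** The data for the comparison are collected, and nothing prevents the analysis from being added.

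**Conclusion.** There is a gap between the comparative safety objective and the planned analysis of fasting glucose, HOMA and HbA1c. No between-treatment difference, interval or adjustment for the screening value is specified for them. The absence is a matter of text and needs no assumption. The size of the benefit does: about 6% to 28% lower variance than the unadjusted difference in mean change, for an assumed r of 0.7 down to 0.3, equal variances, 11 to 12 children per arm and non-prognostic factors. The larger benefit is that the uncertainty, at about ±0.6 to 0.9 SD per pair, would be visible. It is a cheap improvement of minor priority.

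**What to change.** In 10.3.2, keep the descriptive tables and add one paragraph. For each of the three endpoints at week 26 (SAS, on-treatment period), fit an ANCOVA on change from screening, with the screening value as covariate and the factors already used for bone age: treatment, age group, sex, region and sex by age group. Report the four contrasts of the primary analysis with 95% CIs and no p-values.

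Three details should be stated:
- **Model.** Name ANCOVA as the single model. An MMRM would need intermediate visits to be specified, and the flowchart notes that HbA1c is not collected at visit 3.
- **HOMA.** Analyse it on the log scale as a declared choice, with the log screening value as covariate, and say which HOMA index is meant. Section 4.3.2.4 gives the unit as % and Appendix 2 says only that it will be calculated.
- **Missing values.** Children without a week-26 on-treatment value are left out, in line with the bone-age rule.

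The cost is one paragraph and three model outputs, with no new data or visits. The downside is 3 × 4 = 12 more exploratory intervals without multiplicity adjustment, and wide ones. They should be labelled as estimates, not as evidence of equal safety.
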